5.2 RANDOMIZATION

Subjects will be randomized to one of TWO GROUPS: **Group A:** Forty (40) patients will receive GF 1 mg orally; OR, **Group B:** Forty (40) patients will receive a similar appearing placebo (containing no drug) from numbered study drug envelopes (SDE) prepared by Vanderbilt's Investigational Pharmacy Service (IPS) which will independently randomize the drug envelopes and maintain the Master Drug Study Log.

5.3 POWER ANALYSIS

5.4 STUDY METHODS

5.41 PRE-OP

a. **Consent; Demographics;** ²⁵

b. **NO PRE-OP ADJUNCTS**

Ketamine, gabapentin, acetaminophen, droperidol, promethazine, haloperidol, other buterophenones or phenothiazines will not be administered.

5.42 ANESTHESIA MANAGEMENT

The general anesthetic administered will be standardized as follows:

a. **Premedication:** Midazolam 0 - 2 mg IV

b. **Induction:** Fentanyl: 0.5-2 mcg/kg; Lidocaine: 1-2 mg/kg; Propofol: 1-3 mg/kg; SUX: 0.5-1.5 mg /kg

c. **Maintenance:** with inhalational agent and hydromorphone.

d. **Emergence:** Hydromorphone in 0.25 mg increments as deemed appropriate by anesthesia team and a standardized dose of ondansetron (4 mg) in keeping with routine practice.

5.43 PACU: Hydromorphone for pain and ondansetron for PONV per standardized order set will be administered and documented. IV fluids and oxygen may be continued as long as deemed useful by the PACU and Study staff.

5.5 POST-OP:

A. **PONV** will be quantified by the maximum nVRS.

B. **PAIN** will be evaluated by the maximum Verbal Analog Scale (VAS = 0 – 10: See Fig. 6).

C. **PACU LOS** will be the duration of PACU Length of Stay

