Guanfacine for PONV and Pain
After Sinus Surgery
Version: March 10, 2016
NCT #: NCT02882854

Principal Investigator: [name]
Assistant Professor
Department of Anesthesiology
Vanderbilt University Medical Center

Department of Anesthesiology
Vanderbilt University Medical Center

Table of Contents:**Study Schema**

- Abstract**
- 1.0 Background**
- 2.0 Rationale and Specific Aims**
- 3.0 Inclusion/Exclusion Criteria**
- 4.0 Enrollment/Randomization**
- 5.0 Study Procedures**
- 6.0 Risks of Investigational Agents (side effects)**
- 7.0 Reporting of Adverse Events or Unanticipated Problems involving Risk to Participants or Others**
- 8.0 Study Withdrawal/Discontinuation**
- 9.0 Privacy/Confidentiality Issues**
- 10.0 Follow-up**
- 11.0 Record Retention**
- 12.0 References**
- 13.0 Testing Regimens**
- 14.0 Data Dictionary**
- 15.0 Patient Data Sheet**

STUDY SCHEMA

| PRE-OP | SURGERY | EMERGE | PACU |
|--------------------|-------------|-----------|----------|
| Consent | Tot GA time | Extubate | Max nVRS |
| Demographics | #pressors | Transport | PONV Tx |
| Study Drug/placebo | | | Max pVAS |
| | | | Total ME |
| | | | PACU LOS |

After meeting I/O criteria pre-operatively, patients will hear a brief description of the study (guanfacine for PONV). If they are interested, potential participants will be given a consent to read and ask questions. After all their questions have been answered, they will sign the consent if they wish to participate. Study drug will be administered with a few sips water. IV pre-med should consist of no more than 2 mg midazolam.

Total time under general anesthesia (induction to extubation) will be recorded along with the number of times pressors are administered. No non-depolarizing muscle relaxant will be administered to avoid the need for reversal agents and the associated confounding factor.

In PACU, the maximum nausea score (nVRS) 0-10 will be recorded, where 0 = none and 10 = maximum, along with the number of times an anti-emetic is required. Maximum pain score (VAS) along with morphine equivalents will also be recorded. PACU length of stay (LOS) will also be recorded. PACU times may be obtained from the PACU records.

Abstract

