2.5 Hypothesis

As a primary endpoint, we hypothesize that patients undergoing a standardized general anesthetic for sinus surgery and are randomized to receive GF vs Placebo will have 20-30% lower PONV scores in PACU, as measured by the 10-point nausea scale (nVRS) previously used in other studies. Secondly, we hypothesize that patients receiving GF will have less pain as measured by visual/verbal analog (VAS) scores and total morphine equivalents (ME) administered in PACU than patients receiving placebo, without significant hemodynamic instability.

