5.0 Study Procedures

5.1 Statistical Analysis and Power

The effect of guanfacine administration on pain and nausea scores will be assessed using proportional odds logistic regression. The odds of greater pain or nausea associated with guanfacine administration will be summarized using the odds ratio and Wald-type 95% confidence interval and Wald test against the null hypothesis of no effect (odds ratio equal to one).

The study design and testing procedure were simulated to study the statistical power. The distribution of pain and nausea scores in the placebo and guanfacine groups were assumed to have the distributions illustrated in the figure below, which correspond to a difference in mean score of 1.5 points, or an (ordinal) odds ratio of 0.25. Taking this as the minimum detectable effect, **80** randomized subjects are needed to achieve 90% power.

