5.6 DATA COLLECTION (See Data Sheet and Data Dictionary)

- A. STANDARD ANESTHESIA PRE-OP ASSESSMENT
- B. ANESTHESIA RECORD COPY
- C. COPY OF SIGNED PATIENT CONSENT FOR STUDY
- D. PATIENT DATA SHEET, (PDS) including Transition Times:**
 - 1. Planned Surgical Procedure, Duration
 - 2. Demographics (age, height, weight, etc.)
 - 3. Nausea score (nVRS) and rescue Tx in PACU
 - 4. Pain Scores (VAS) and Tx in PACU
 - 5. PACU LOS

5.7 STUDY CONDUCT:

5.71 PRE-OP: After soliciting interest and enrolling, **written consent** will be obtained and basic patient data and pre-op assessments (Apfel Score **Fig 2**) performed. Patients will receive GF or placebo orally from a numbered envelope prepared by the IPS in a blinded manner. Patients will then undergo a standardized general anesthetic as described above. At the conclusion of the sinus procedure, patients will be extubated as per routine management and assessed immediately with:

5.72 In PACU, assess the following endpoints:

- A. Max Nausea score (nVRS)
- B. PONV Treatment(s)
- C. VAS (Fig 6): Assess Pain score (Verbal Analog Scale rated 1-10) at 10 and 60 min after PACU arrival
- D. Pain TX: Total Narcotic requirement in PACU (Tallied in Morphine Equivalents for PACU stay)
- E. PACU LOS

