13.0 Testing Regimens

Fig 3. Verbal/Visual Analog Pain Score (VAS) ²⁹:

NO PAIN ----- WORST PAIN
 0-----1-----2-----3-----4-----5-----6-----7-----8-----9-----10

At 10, 30, and 60 min after PACU arrival ask patient to verbally score their pain on this scale.

Data Dictionary-

1. Patient Data Sheet, (PDS) will include all data collected on each individual:

A. Planned Surgical Procedure (all sinus surgeries not greater than 3 hours)

B. Demographics: Data identifying characteristics of each patient, including

Age, Gender, Height, Weight, MRN, etc.)

2. POST-OP:

A. Anesthetic Duration – Difference between induction and extubation recorded in the Anesthesia Record; PACU Entry Time

B. PONV will be quantified by a Nausea Verbal Reporting Scale (nVRS), 0-10

C. PAIN will be evaluated by Verbal Analog Scale (VAS = 0 – 10). (See Fig. 3)

D. PACU LOS

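### Maximum PACU pain can miss early peaks: no score is required at arrival or before a rescue dose, which may dilute the VAS comparison

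*Combined protocol and SAP*

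**What the plan says.** The pain score is described in three ways.

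- **Untimed maximum.** The Study Schema text says "Maximum pain score (VAS) along with morphine equivalents will also be recorded", and section 5.5B says pain "will be evaluated by the maximum Verbal Analog Scale (VAS = 0 – 10: See Fig. 6". Neither gives rating times or says whose scores count.
- **Two ratings.** Section 5.72C: "Assess Pain score (Verbal Analog Scale rated 1-10) at 10 and 60 min after PACU arrival".
- **Three ratings.** Section 13.0, under Fig 3: "At 10, 30, and 60 min after PACU arrival ask patient to verbally score their pain on this scale".

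Section 5.71 states that "patients will be extubated as per routine management and assessed immediately with", but the list that follows is the PACU list, whose only timed pain ratings are those of 5.72C. Nausea is the maximum nVRS in PACU, with no rating times.

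On rescue, section 5.43 says "Hydromorphone for pain and ondansetron for PONV per standardized order set will be administered and documented". The order set's triggers, timing and scoring requirements are not in the documents. Sections 5.6 D and 5.72 B and D collect PACU treatment for nausea and pain, the latter as morphine equivalents.

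On analysis, section 5.1 says "The effect of guanfacine administration on pain and nausea scores will be assessed using proportional odds logistic regression". It gives no method for morphine equivalents and does not mention rescue. Section 2.5, however, rests the secondary hypothesis on "less pain as measured by visual/verbal analog (VAS) scores and total morphine equivalents (ME) administered in PACU".

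**The concern.** Hydromorphone is given to bring down the score that is being compared. Where the timed schedule is followed as written, a patient in severe pain soon after arrival can be dosed before the 10-minute rating, or between later ratings, and the recorded maximum is then a value after treatment. If guanfacine reduces pain, more placebo than guanfacine patients reach a level that prompts treatment, so more placebo peaks can be lost. The recorded odds ratio would then move toward 1.

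The analysis plan has a matching gap. Section 2.5 uses VAS and opioid use together, but 5.1 tests only the scores. The plan does not say what to conclude if the arms show equal VAS with less opioid on guanfacine, or lower VAS with more opioid. A peak that was never recorded cannot be recovered later, and a rule for reading VAS with opioid use would carry little weight if chosen after unblinding.

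**Working it through.** **Inputs from the documents.** Odds ratio 0.25, or a mean difference of 1.5 points; 80 randomized for 90% power (5.1); 40 per arm (5.2). Two-sided 0.05 is taken from the 95% interval in 5.1.

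**Inputs assumed.** The placebo distribution (the plan's is in a figure not available in the text), the score at which early treatment becomes possible (4 or more), the share of such patients treated before rating, and the drop in the recorded score.

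**The plan's own figure.** The proportional odds sample size formula is N = 12(z₁ + z₂)² / [(log OR)² (1 − Σp̄³)], where p̄ is the average probability of each score over the two arms. Take placebo pain as a discretised logistic on 0–10 (location 4.5, scale 1.1, SD 1.94). The guanfacine mean is then 1.47 lower and Σp̄³ = 0.022.

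- 12 × (1.960 + 1.282)² = 126.1, and (log 0.25)² = 1.922.
- N = 126.1 / (1.922 × 0.978) = 67.
- Power with 80 patients: √(80 × 1.922 × 0.978 / 12) − 1.96 = 1.58, which gives 94%.

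Other placebo distributions without a large share of zeros give 66 to 81. So 80 is plausible, but it cannot be reproduced exactly without the figure.

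**Direction of the effect.** On this placebo distribution:

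- Share scoring 4 or more on placebo: 1 / (1 + exp(−(4.5 − 3.5)/1.1)) = 0.713, which is odds of 2.48.
- On guanfacine the odds are 0.25 × 2.48 = 0.62, a share of 0.383.
- If a share f of these patients is treated before rating and the score drops by d, the mean difference becomes 1.47 − f × d × (0.713 − 0.383).
- With f = 0.5: 1.47 − 0.33 = 1.14 for d = 2, and 1.47 − 0.50 = 0.97 for d = 3.

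**Effect on power (simulation, 40 per arm).** Column A is the logistic placebo above with a tie-corrected rank test, 4,000 trials per row. Column B is a roughly normal placebo (mean 5, SD 2) with the proportional odds Wald test, 300 trials per row, so its standard error is about √(0.83 × 0.17 / 300) = 2 percentage points.

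| Share treated before rating | Drop | A: OR, power | B: OR, power |
|---|---|---|---|
| none | – | 0.25, 94% | 0.25, 93–94% |
| 25% | 2 | 0.28, 88% | 0.29, 91% |
| 25% | 3 | 0.33, 80% | not run |
| 50% | 2 | 0.31, 83% | 0.29, 83% |
| 50% | 3 | 0.40, 62% | 0.37, 64% |
| all | 2 | not run | 0.31, 80% |

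In B at a 50% share and a 2-point drop, 39% of placebo and 23% of guanfacine patients were treated before rating. Moving the logistic placebo location to 3.5 or 5.5 gives 86% and 84% (2-point drop) or 74% and 65% (3-point drop) at a 50% share, so location 4.5 gives the largest loss of the three. If the score before rescue is recorded and counted, this loss is zero.

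**Nausea.** With 35% of placebo at zero, OR 0.25, and half of scores of 3 or more treated before rating, power goes from 91% to 90–86% for a 2 to 3-point drop. It reaches 74% only with a 5-point drop.

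**The case against.** Much of the case on the other side stands.

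- **Timing of rescue.** A reader might infer that hydromorphone is given on demand from arrival and that the worst pain is routinely treated before it is scored. The documents do not say this. The order set is not shown and may itself require a score before each dose.
- **Untimed maximum.** The Study Schema and 5.5B define pain as a maximum without clock times. If charted nursing scores count, a charted peak before dosing is kept. But the plan neither requires such a score nor says that it counts.
- **Estimand.** Section 8.2 calls the design intention-to-treat. As a comparison under usual rescue, a smaller VAS difference is a valid result. It is diluted only as a measure of pain before rescue. The plan does not say which is meant, and in either case VAS has to be read with opioid use.
- **Power.** A reader might infer that the stated 90% is not delivered. That is not shown. The OR of 0.25 may already describe scores recorded under usual care, and every rescue input above is assumed.
- **Morphine equivalents.** They are collected and named in 2.5, so unequal rescue would be visible. What is missing is a method and a rule for reading the two results together.
- **Emergence opioid.** Hydromorphone is also given at emergence (5.42d), so an arrival rating would not make opioid exposure equal.

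What remains is that three descriptions of one endpoint conflict, and that none of them secures the score before rescue.

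**Conclusion.** The concern holds as a gap in measurement and analysis, not as a demonstrated bias. Followed as written, the timed schedules can miss pain treated before a rating. If guanfacine works, the loss would fall more on placebo and pull the VAS odds ratio toward 1. Both simulations agree on that direction.

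The size is unknown. On the assumed inputs it runs from a small loss (88% to 91% power with a quarter treated and a 2-point drop) to a substantial one (62% to 64% with half treated and a 3-point drop).

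It would be tempting to extend the point in full to the primary nausea score. The documents do not support that: nVRS is an untimed maximum, so the delay to a 10-minute rating does not apply, and the illustrated loss is modest. The point concerns mainly a secondary endpoint. It is worth acting on because the remedy is cheap and the missing scores cannot be recovered.

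**What to change.** 1. Reconcile 5.5B, 5.72C and 13.0 to one VAS schedule. In the same edit settle the scale (1–10 in 5.72C, 0–10 elsewhere) and the figure reference (Fig. 6 or Fig. 3).
2. Add a VAS rating at PACU arrival and immediately before each PACU hydromorphone dose, and an nVRS rating immediately before each PACU anti-emetic dose. State that these count toward the maximum. Rescue treatment itself is unchanged.
3. In 5.1, add a comparison of PACU morphine equivalents between arms, for example by a rank-based or proportional odds test, reported beside VAS. State that lower VAS with higher morphine equivalents will not be described as less pain.
4. Optional, as sensitivity analyses only: a sum of the VAS and morphine-equivalent ranks, and a nausea analysis that ranks rescued patients above the others. The first weights the two measures equally and lets them cancel. The second would place a rescued nVRS of 2 above an unrescued 10.

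The cost is a short wording change, a few more ratings per patient and extra lines on the Patient Data Sheet. The ratings are taken when a nurse is already at the bedside to give the dose.

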5.6 DATA COLLECTION (See Data Sheet and Data Dictionary)

- A. STANDARD ANESTHESIA PRE-OP ASSESSMENT
- B. ANESTHESIA RECORD COPY
- C. COPY OF SIGNED PATIENT CONSENT FOR STUDY
- D. PATIENT DATA SHEET, (PDS) including Transition Times:**
 - 1. Planned Surgical Procedure, Duration
 - 2. Demographics (age, height, weight, etc.)
 - 3. Nausea score (nVRS) and rescue Tx in PACU
 - 4. Pain Scores (VAS) and Tx in PACU
 - 5. PACU LOS

5.7 STUDY CONDUCT:

5.71 PRE-OP: After soliciting interest and enrolling, **written consent** will be obtained and basic patient data and pre-op assessments (Apfel Score **Fig 2**) performed. Patients will receive GF or placebo orally from a numbered envelope prepared by the IPS in a blinded manner. Patients will then undergo a standardized general anesthetic as described above. At the conclusion of the sinus procedure, patients will be extubated as per routine management and assessed immediately with:

5.72 In PACU, assess the following endpoints:

- A. Max Nausea score (nVRS)
- B. PONV Treatment(s)
- C. VAS (Fig 6): Assess Pain score (Verbal Analog Scale rated 1-10) at 10 and 60 min after PACU arrival
- D. Pain TX: Total Narcotic requirement in PACU (Tallied in Morphine Equivalents for PACU stay)
- E. PACU LOS

6.0 RISKS

Both PONV and post-op pain are expected risks after surgery. The risk of the use of GF include modest hypotension and sedation. Coincident to the study, patients will be undergoing sinus

surgery, but there will be no medical procedures performed on patients as part of the study. To protect the patient's confidentiality, only a limited data set will be created. The PI will check the data for completeness after it's been collected/extracted/collated and verify that all subject identifiers except those listed in the limited data set are destroyed once the study is concluded. All data will be stored on a password-protected server in a locked area of the VUMC Department of Anesthesiology. This data will only be accessible by the PI and KSP.

7.0 Reporting of Adverse Events or Unanticipated Problems involving Risk to Participants or Others

Adverse events will be monitored throughout the study. These may include any occurrence within the study setting (surgery itself or the conduct of the anesthetic), such as unexplained changes in vital signs, unexpected surgical complications, prolonged PACU stay, etc. *Protocol deviations* will be reported separately per VHRPP guidelines. The PI of this study will report adverse events to the IRB per VHRPP reporting guidelines.

8.0 Study Withdrawal/Discontinuation

8.1 Withdrawal. After Study Drug administration, this study involves only assessment for nausea and vomiting (nVRS) and pain (VAS) in the surgical setting of sinus surgery. After patients have been enrolled and consented, it is not anticipated that patients will voluntarily withdraw. Nevertheless, patients are free to withdraw at any time, simply by telling one of the study physicians/managers. However, after enrollment and initial pre-op study assessment, patients may withdraw up to the point of anesthetic induction and surgical procedure, and thereafter, may only withdraw when fully awake and alert in PACU.

8.2 Discontinuation. This study is designed as intention-to-treat, so once subjects have taken the Study Drug, they will be followed per protocol through completion, or up to any time they choose to withdraw or any unspecified Adverse Event that would halt normal data collection. In either event, data obtained to that point in the protocol would be included in the total dataset, with reporting of the withdrawal or AE as noted above.

9.0 Privacy/Confidentiality Issues

All reasonable efforts will be made to keep a patient's protected health information (PHI) private and confidential. Patients will be assigned a code to replace names. There will be limited access to medical records and a limited data set created. Federal privacy guidelines will be followed when using or sharing any protected health information.

Data will be stored in secured areas on password protected Vanderbilt PCs conforming to the latest Vanderbilt IS security policies. Computer databases will be maintained on password protected Vanderbilt PCs. REDCap (see below) servers are housed in a local data center at Vanderbilt, and all web-based information transmission is encrypted. REDCap was developed specifically around HIPAA-Security guidelines and is recommended to Vanderbilt researchers by both our Privacy Office and Institutional Review Board. All study staff have completed employee education regarding patient confidentiality and have completed Human Subjects protection education (CITI course) as specified by the VHRPP.

10.0 Follow-up

The Perioperative Clinical Research Institute (PCRI) will retain research Records for a period of six (6) years after the submission of the final report and closeout procedures on the research project for which the Research Records were prepared. Paper copies of the research records and/or research consent will be held in a secure access area determined by of the Department of Anesthesia (PCRI) for 6 years. Any research data that is put in the participants medical record will be kept for an unknown length of time.

11.0 Record Retention & Data Management

The retention of the original Research Records will be the responsibility of the Principal Investigator on behalf of PCRI, but at all times shall remain the property of PCRI, unless otherwise specified by law, regulation or agreement. The Vanderbilt University Office of Research will be used as a central location for data processing and management. Vanderbilt University, with collaboration from a consortium of institutional partners, has developed a software toolset and workflow methodology for electronic collection and management of research and clinical trial data. REDCap (Research Electronic Data Capture) is a secure, web-based application that is

flexible enough to be used for a variety of types of research. REDCap provides an intuitive user interface that streamlines project development and improves data entry through real-time validation rules (with automated data type and range checks). REDCap also provides easy data manipulation (with audit trails for reporting, monitoring and querying patient records) and an automated export mechanism to common statistical packages (SPSS, SAS, Stata, R/S-Plus). In addition to traditional data capture functionality, all data collection projects rely on a thorough, study-specific data dictionary, defined by all members of the research team in an iterative, self-documenting process. This iterative development and testing process results in a well-planned and individualized data collection strategy.

13.0 Testing Regimens

Fig 3. Verbal/Visual Analog Pain Score (VAS) ²⁹:

NO PAIN ----- WORST PAIN
 0-----1-----2-----3-----4-----5-----6-----7-----8-----9-----10

At 10, 30, and 60 min after PACU arrival ask patient to verbally score their pain on this scale.

Data Dictionary-

1. Patient Data Sheet, (PDS) will include all data collected on each individual:

A. Planned Surgical Procedure (all sinus surgeries not greater than 3 hours)

B. Demographics: Data identifying characteristics of each patient, including

Age, Gender, Height, Weight, MRN, etc.)

2. POST-OP:

A. Anesthetic Duration – Difference between induction and extubation recorded in the Anesthesia Record; PACU Entry Time

B. PONV will be quantified by a Nausea Verbal Reporting Scale (nVRS), 0-10

C. PAIN will be evaluated by Verbal Analog Scale (VAS = 0 – 10). (See Fig. 3)

D. PACU LOS
